The risks of the study are minimized by close communication between study investigators and subjects, careful monitoring of IGF-1 levels, and frequent monitoring for adverse events. The study may provide benefit to individual patients, as above, and is also expected to provide information that may lead to the development of new treatment strategies for NAFLD, which is a significant public health problem. Therefore, benefits are felt to outweigh the risks.

IX. Adverse Event, Unanticipated Problem, and Deviation Definitions

Adverse Event (AE)

An adverse event is any untoward or unfavorable medical occurrence in a human subject, including any abnormal sign (e.g., abnormal physical exam or laboratory finding), symptom, or disease, temporally associated with the subject's participation in the research, whether or not considered related to the research.

Adverse Reaction (AR)

An adverse event that is caused by an investigational agent (drug or biologic).

Suspected Adverse Reaction (SAR)

An adverse event for which there is a reasonable possibility that the investigational agent caused the adverse event. 'Reasonable possibility' means that there is evidence to suggest a causal relationship between the drug and the adverse event. A suspected adverse reaction implies a lesser degree of certainty about causality than adverse reaction which implies a high degree of certainty.

Serious Adverse Event (SAE)

A Serious Adverse Event is an AE that results in one or more of the following outcomes:

- death
- a life threatening (i.e., an immediate threat to life) event
- an inpatient hospitalization or prolongation of an existing hospitalization
- a persistent or significant incapacity or substantial disruption of the ability to conduct normal life functions
- a congenital anomaly/birth defect
- a medically important event*

* Medical and scientific judgment will be exercised in deciding whether expedited reporting is appropriate in other situations, such as important medical events that may not be immediately life threatening or result in death or hospitalization but that may jeopardize the subject or may require intervention to prevent one of the other outcomes listed above.

Serious Adverse Drug Reaction (SADR)

An SADR is defined as a serious adverse event that has a reasonable suspected causal relationship to the study drug. For the purposes of reporting during this protocol, any serious adverse event occurring in a subject randomized to study drug that is judged by the investigator to be *possibly related, probably related, or definitely related* (see below) to study drug will be considered in this category.

Unexpected Adverse Event

An AE is unexpected if it is not listed in the Package Insert for norditropin or is not listed at the specificity or severity that has been observed.

Unanticipated Problem (UP)

An Unanticipated Problem is any event, incident, experience, or outcome that is

1. unexpected in terms of nature, severity, or frequency in relation to
 - a. the research risks that are described in the IRB-approved research protocol and informed consent document; Investigator's Brochure or other study documents; and
 - b. the characteristics of the subject population being studied; and
2. possibly, probably, or definitely related to participation in the research; and
3. places subjects or others at a greater risk of harm (including physical, psychological, economic, or social harm) than was previously known or recognized.

Protocol Deviation: Any change, divergence, or departure from the IRB approved study procedures in a research protocol. Protocol deviations are designated as serious or non-serious and further characterized as

1. Those that occur because a member of the research team deviates from the protocol.
2. Those that are identified before they occur, but cannot be prevented.
3. Those that are discovered after they occur

Pregnancy will be reported as described below if it occurs in any subject receiving norditropin or if it occurs in a subject's partner whose fetus or baby develops an adverse event considered to be related to norditropin.

Relatedness will be determined as follows:

Definitely Related

- reasonable temporal relationship

- follows a known response pattern
- clear evidence to suggest a causal relationship
- there is no alternative etiology

Probably Related

- reasonable temporal relationship
- follows a suspected response pattern (based on similar agents)
- no evidence of a more likely alternative etiology

Possibly Related

- reasonable temporal relationship
- little evidence for a more likely alternative etiology

Unlikely Related

- does not have a reasonable temporal relationship
OR
- good evidence for a more likely alternative etiology

Not Related

- does not have a temporal relationship
OR
- definitely due to an alternative etiology

X. Reporting Requirements

[name] (PI) will be responsible for the reporting of adverse events, unanticipated problems, protocol deviations, and other necessary events as follows:

Reporting to Novo Nordisk

Serious Adverse Drug Reactions and pregnancies will be reported to Novo Nordisk as soon as possible and no later than 7 days following investigator awareness of the event. [name] will assist Novo Nordisk with follow-up of any reports as necessary.

Reporting to IRB (Partners Human Research Committee)

The following will be reported within 7 calendar days of investigator awareness:

- Internal adverse events that are unexpected, and related or possibly related to the research and that indicate there are new or increased risks to subjects
- Deviation from the approved research protocol or plan without IRB approval in order to eliminate apparent immediate hazard to subjects or harm to others
- Deviation from the approved research protocol or plan that placed subjects or others at an increased risk of harm regardless of whether there was actual harm to subjects or others
- Breach of confidentiality or violation of HIPAA (e.g., lost or stolen laptop)
- Medication, procedural or laboratory error (e.g., errors in drug administration or dosing, surgical or other procedure, or testing of samples or test results) regardless of whether subjects experienced any harm
- Interim analysis, safety monitoring report, publication in a peer-reviewed journal, or other finding that indicates that there are new or increased risks to subjects or others or that subjects are less likely to receive any direct benefits from the research
- Change in FDA labeling (e.g., black box warning), withdrawal from market, manufacturer alert from Novo Nordisk, or recall of an FDA-approved drug, device, or biologic used in the research

- Complaint by/on behalf of a research subject that indicates that the rights, welfare, or safety of the subject have been adversely affected or that cannot be resolved by the investigator
- Incarceration of a research subject during participation in research that is not approved for involvement of prisoners as subjects
- Noncompliance with applicable regulations or requirements or determinations of the IRB identified by the research team or others (e.g., FDA Form 483 or Warning Letter) that indicates that the rights, welfare, or safety of subjects have been adversely affected
- Suspension or termination of the research, in whole or in part, based on information that indicates that the research places subjects at an increased risk of harm than previously known or recognized (e.g., FDA clinical hold)
- Suspension or disqualification of an investigator by FDA, Novo Nordisk, or others
- Scientific misconduct
- Any other problem that indicates that the research places subjects or others at an increased risk of harm or otherwise adversely affect the rights, welfare or safety of subjects or others.

The following items will be reported to the MGH IRB in summary at the time of Continuing Review:

- Serious and non-serious unanticipated problems
- Expected serious adverse events that are possibly, probably, or definitely related to the research
- Serious adverse events that are not related to the research
- All adverse events
- Serious and Non-Serious Protocol deviations
- Serious, continuing, and minor non-compliance
- Any trends or events which in the opinion of the investigator should be reported

XI. Monitoring and Quality Assurance

Full IRB approval will be obtained by the Partners Human Research Committee before any interactions with subjects take place for the purposes of this protocol. The protocol will be conducted adhering to the standards of Good Clinical Practice.

Written, informed consent will be obtained prior to any procedures being performed on a subject for the purposes of this protocol. This consent will be obtained by a licensed medical provider (MD or NP).

The principal investigator ([name]) will monitor all data collected for the studies. Data will be stored securely, with access restricted to co-investigators and study staff. Binders with subject information will be labeled with a coded enrollment number to protect confidentiality. Electronic databases will be locked and password-protected, with access available only to study staff. Data will not be saved on the hard drive of any laptop or desktop computers or on any removable data storage devices such as flash drives or CDs.

The risks to subjects will be minimized by using procedures which are consistent with sound research design. Subjects will be carefully screened to minimize potential risk of study procedures and treatments. A pregnancy test will be performed at each visit for female subjects of childbearing potential, and patients who become pregnant will be asked to discontinue participation in the study. Most importantly, the safety of subjects will be monitored closely by the principal investigator, co-investigators and DSMB, and subjects will be discontinued from the study if the risk to the subject is felt to be excessive.

Data and Safety Monitoring Plan

An independent data and safety monitoring board will be established to review safety data and adverse events. The DSMB will include a statistician, a gastroenterologist, and a pediatric endocrinologist, and will meet every 6 months. The studies will also be monitored continuously by the principal investigator ([name]).

Subjects will be instructed to report any adverse events immediately. A physician or nurse practitioner will be available on-call 24 hours/day, 7 days/week, to all study participants for any questions or concerns.

Clinical Trials Registration

The trial will be registered on clinicaltrials.gov, with [name] serving as the responsible party for registration and reporting of results.

XII. Dissemination of Results

Upon completion of the protocol, an abstract summarizing the primary results will be submitted to an appropriate national meeting (e.g., Pediatric Academic Societies or ENDO), and a manuscript comprehensively reporting the results will be submitted to an appropriate journal (e.g., *Journal of Clinical Endocrinology and Metabolism*). Preparation and submission of the primary manuscript reporting results is anticipated to be complete within 4 months of the last study visit for the last patient.

XIII. References Cited

1. [name] TL, Levitsky LL, Grinspoon SK, [name] M. Effect of body mass index on peak growth hormone response to provocative testing in children with short stature. *J Clin Endocrinol Metab.* 2009 Dec;94(12):4875-81.

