 - b. Compared to no treatment, Norditropin will significantly reduce markers of hepatocellular injury and steatohepatitis, including transaminases, gamma glutamyl transferase (GGT), and cytokeratin -18 (CK18).
2. **Physiologic replacement of GH with Norditropin will be neutral to glucose homeostasis and will improve other measures of cardiometabolic risk.**
 - a. Fasting and 2-hour glucose, HOMA-IR, and Matsuda index will not be significantly different from baseline after 24 weeks of Norditropin treatment
 - b. Norditropin will result in a reduction in VAT (measured by MRI) and trunk fat (measured by DXA) compared to no treatment
 - c. Norditropin will result in an increase in adiponectin and a reduction in CRP compared to no treatment

III. Subject Selection

24 obese young adults (M and F) with liver fat $\geq 5\%$ on ^1H -MRS and relative reduction in GH but without a known clinical diagnosis of growth hormone deficiency will be recruited for the RCT. We anticipate screening up to 150 subjects to identify 24 who meet enrollment criteria. Relative reduction in GH will be assessed by IGF-1 z-score, with subjects whose IGF-1 z-scores are ≤ 0 eligible for the study. Many previous studies have defined relative GH deficiency as an IGF-1 z-score ≤ 0 (68, 69).

Inclusion criteria:

1. Males and Females ages 18-29yo
2. BMI $\geq 95^{\text{th}}$ percentile and/or $\geq 30\text{kg}/\text{m}^2$
3. Hepatic fat $\geq 5\%$ by ^1H -MRS
4. IGF-1 standard deviation score (SDS) ≤ 0

Exclusion criteria:

1. Alcohol consumption of >14 drinks per week (F) or >21 drinks per week (M) (40)
2. Use of insulin or oral anti-diabetic medications, or HbA1c $>7\%$ or fasting glucose $\geq 126\text{mg}/\text{dL}$
3. Use of corticosteroid, gonadal steroids, or methotrexate ≤ 3 months prior to baseline visit
4. Known diagnosis of alpha-1 antitrypsin deficiency, Wilson's disease, hemochromatosis, or autoimmune hepatitis
5. HgB < 11.0 g/dL or wt $< 50\text{kg}$
6. AST or ALT $>2.5\text{x}$ upper limit of normal (ULN), total bilirubin $> \text{ULN}$, positive Hep B sAg, or Hep C Ab
7. Routine MRI exclusion criteria (including weight >450 lbs)
8. Use of weight-loss medications or previous weight loss surgery
9. Pregnant or breastfeeding, or, for sexually-active females, unwillingness to use an appropriate form of contraception during the study

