Analysis will be intention-to-treat, using all available data from all subjects. Wilk-Shapiro test will be used to assess for normality of distribution of all variables, and variables that are not normally distributed will be appropriately transformed. Baseline variables will be compared between treatment groups, and any baseline variable that is statistically different between treatment groups will be adjusted for in subsequent analysis. Changes in variables measured only at baseline and 6 months, including the primary endpoint of liver fat, will be initially assessed using a two-sample t-test comparing mean changes between treatment groups. A critical alpha level of 0.05 will be used as the threshold for significance, and all statistical tests will be two-tailed. Subsequently, adjusted analyses will be performed including as covariates any baseline characteristics that differ between treatment groups and any differential changes in nutritional intake or physical activity between treatment groups over the study duration. For variables measured at ≥ 3 timepoints throughout the study (e.g., IGF-1, AST and ALT), we will analyze the longitudinal data using general linear mixed effects modeling, testing for time x treatment group interaction. The primary analysis will be an intention to treat analysis using all available data. We will consider secondary multiple imputation based analyses if necessary.

A supplementary analysis will be performed assessing stimulated growth hormone levels in response to Arginine testing. Using peak GH as the independent variable, we will assess the hypothesis that peak GH will be negatively associated with liver fat quantity.

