Sample Size and Power Calculations: The study is designed to yield pilot data, with the primary endpoint being change in hepatic fat fraction. As we do not have preliminary data on this measure in an adolescent population, we used a published standard deviation (SD) of 3.1%. A sample size of 24 subjects, with up to 20% discontinuation rate, yielding 19 evaluable patients, has 80% power to detect a 4.2 percentage point treatment effect on liver fat (e.g., a reduction from 7% liver fat to 2.8% liver fat), which is the minimum difference that would be clinically relevant, as absolute reductions of ≥ 4 -5% liver fat have been considered clinically relevant in previous publications (77, 78). For secondary variables of interest, the study is has 80% power to detect a treatment difference of approximately 1.4 SD.

VIII. Risks and Discomforts

Radiation: Subjects will have 2 DXA scans over 6 months, for a total radiation risk from both scans of 2 microSieverts. This radiation exposure is minimal and does not pose excessive risk to subjects. Female subjects must have a negative pregnancy test before DXA scanning.

Blood Drawing: Blood sampling volumes will be as follows: screen 27cc, baseline and 24 week visit 99cc, safety visits 5-8cc each (5 cc at 2 and 4 weeks, 8cc at 6, 12, 18 weeks). The total blood drawing will be 286cc over 6 months. The maximum blood drawn during any 8 week period (screen+baseline+2wk+4wk) will be no more than 140cc. Body weight ≥ 50 kg and Hgb ≥ 11 g/dL will be required to participate, which will ensure that the blood volume sampled is within guidelines and does not pose significant risk to subjects.

Blood drawing may cause discomfort, pain, and bruising.

MRI/MR spectroscopy: MRI and MR spectroscopy will be performed using FDA approved devices and pulse sequences, and there are no known foreseeable risks associated with exposure to MRI. Subjects will be carefully screened for the presence of metallic implants (e.g., vascular clamps) prior to MR scanning. Some

subjects report claustrophobia during MRI scans, and if any patient experiences discomfort during the scan, the procedure will be aborted and not repeated without the subject's consent.

Oral Glucose Tolerance Test: Oral glucose tolerance test has no significant risks. Some subjects may experience nausea or lightheadedness during the procedure, and supportive nursing care will be provided.

Clonidine/Arginine Stimulation:

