- s/he has fasting glucose ≥ 126 mg/dL confirmed on a repeat draw
- s/he reports significant adverse effects including significant arthralgia, myalgia, or edema

The study will be stopped if

- More than 2 individuals in the GH group have persistent fasting glucose ≥ 126 mg/dL

The study will be halted and the dosing algorithm reconsidered (and lowered) if

- More than 2 individuals in the GH group have IGF-1 SDS >2 after 2 dose reductions

Alternative Treatments

There are no FDA-approved highly effective treatments for NAFLD in young adults, and research into novel treatments is urgently needed. Vitamin E, ursodiol, and metformin are sometimes used for NAFLD, and vitamin E has been demonstrated to improve liver histology in individuals with NASH. Subjects who wish to participate and have been receiving Vitamin E or ursodiol at a stable dose for ≥ 6 months will be eligible for the study with continued use of these medications (under the ongoing care of their hepatologist) during the study. Metformin use is not allowed as it will confound assessment of glucose homeostasis. We will not ask any subject to discontinue any medication in order to participate in the study.

As we are not performing liver biopsy during the current study, the study procedures will not result in new diagnosis of NASH (which requires histology). However, subjects without known NAFLD who demonstrate $\geq 5\%$ liver fat on MRS and who have elevated ALT or AST are likely to have NASH, and, if not already under the care of a hepatologist, these subjects will be offered a clinical referral to pediatric hepatology. Subjects who are found to have labs suggesting significant liver disease (AST or ALT > 2.5x upper limit of normal (ULN) or total bilirubin > ULN) will be encouraged to seek clinical care from a hepatologist and will not be eligible for the study. AST and ALT will be carefully monitored (0, 6, 12, 18, and 24 weeks).

VIII. Potential Benefits

Participants will receive information about their nutritional and metabolic health. In addition, subjects randomized to Norditropin may experience benefits from this treatment including decrease in fat mass and possibly decreases in liver fat and systemic inflammation. All subjects will receive lifestyle counseling and information about healthy nutrition and physical activity. Further, the information obtained from this study will inform the potential use of rhGH and possibly other strategies to treat NAFLD in adolescents.

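### Aim 2a equates glucose neutrality with no significant change from baseline on Norditropin; this conflicts with the between-arm analysis in Section VII, and a non-significant result on either test would not show neutrality

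*Combined protocol and SAP*

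**What the plan says.** Section II, Aim 2 states: "Physiologic replacement of GH with Norditropin will be neutral to glucose homeostasis". Aim 2a gives the content: fasting glucose, 2-hour glucose, HOMA-IR and Matsuda index "will not be significantly different from baseline after 24 weeks of Norditropin treatment". The other sub-aims (1a, 1b, 2b and 2c) are all set against the control arm; Aim 2c, for example, reads "Norditropin will result in an increase in adiponectin and a reduction in CRP compared to no treatment". Aim 2a alone is not.

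Section VII uses a different contrast. Variables measured only at baseline and 24 weeks "will be initially assessed using a two-sample t-test comparing mean changes between treatment groups". For variables with three or more timepoints, "we will analyze the longitudinal data using general linear mixed effects modeling, testing for time x treatment group interaction". Tests are two-sided at 0.05. The secondary endpoints listed there include fasting and 2-hour glucose and insulin, and HbA1c. HOMA-IR and Matsuda index are not named.

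On size, Section VII says: "A sample size of 24 subjects, with up to 20% discontinuation rate, yielding 19 evaluable patients". For secondary variables it claims "80% power to detect a treatment difference of approximately 1.4 SD". No margin, confidence-interval rule or power statement is attached to Aim 2a.

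**The concern.** There are two separate problems.

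1. **Contrast.** Aim 2a looks at change from baseline in the treated arm, although the trial randomises a no-treatment arm. Section VII compares arms. Nothing says which governs a statement about Aim 2. The difference matters because, under Potential Benefits, "All subjects will receive lifestyle counseling and information about healthy nutrition and physical activity". A within-arm change therefore mixes any effect of counselling, or of time, with the effect of the drug.

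2. **Inference.** Non-significance is treated as the mark of no effect. In a small sample it is the likely result even when a moderate change is real. Moving to the Section VII test repairs the first problem and leaves the second.

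At stake is whether the report can call Norditropin neutral for glucose. Section VIII lists hyperglycemia among the possible side effects, and Section I says pediatric studies will follow if this pilot shows benefit. An unsupported statement of neutrality could carry into that decision.

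**Working it through.** **Inputs from the documents.** 24 subjects randomised 1:1 (Section V), so 12 per arm. 19 evaluable (Section VII), taken as 9 v 10. Two-sided alpha 0.05. SD 3.1 and effect 4.2 percentage points for liver fat.

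**Assumptions.** No SD for glucose change is given, so effects are in units of the SD of change. 0.5 SD is illustrative, and larger values are shown beside it. Changes are taken as normal with equal variance, and the treated arm as 9 to 12.

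**Step 1. The plan's own figure.** Two-sample t-test, 9 v 10, df = 17.
- Standard error in SD units: √(1/9 + 1/10) = 0.459.
- Liver fat: 4.2/3.1 = 1.355 SD, noncentrality 1.355/0.459 = 2.95, power 79%.
- 80% power is reached at 1.37 SD.

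Both agree with the stated 80% and approximately 1.4 SD, so the plan's power figures reproduce.

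**Step 2. Aim 2a as worded.** Paired t-test in the treated arm, noncentrality δ√n, df = n − 1. At δ = 0.5 and n = 9 the noncentrality is 1.50 against a critical value of 2.306. The 95% CI half-width is t(0.975, n − 1)/√n.

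| n treated | Non-significant, true 0.5 SD | 0.8 SD | 1.0 SD | 95% CI half-width |
|---|---|---|---|---|
| 9 | 74% | 44% | 25% | 0.77 SD |
| 10 | 71% | 38% | 20% | 0.72 SD |
| 12 | 65% | 29% | 12% | 0.64 SD |

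These are per measure. If neutrality needs all four measures to be non-significant, a common 0.5 SD worsening still passes 18% to 55% of the time (simulation; n = 12 to 9, assumed correlation 0 to 0.8). If only one of the four worsens by 0.5 SD, the rule passes 55% to 68% of the time.

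**Step 3. Section VII's between-arm t-test.** At 9 v 10 and δ = 0.5, the noncentrality is 0.5/0.459 = 1.09 against a critical value of 2.110.
- Non-significant: 82% at 0.5 SD, 62% at 0.8 SD, 46% at 1.0 SD.
- 95% CI half-width: 2.110 × 0.459 = 0.97 SD.

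An observed difference of zero would therefore still be compatible with a true difference of nearly 1 SD either way.

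**Step 4. What a margin rule would deliver.** 9 v 10, no true effect, per measure. One-sided: the 95% CI excludes a worsening beyond the margin. Two-sided equivalence: the 90% CI lies within both limits.

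| Assumed margin | One-sided rule met | Equivalence met |
|---|---|---|
| 0.5 SD | 18% | 0.1% |
| 1.0 SD | 54% | 35% |
| 1.4 SD | 82% | 80% |

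For scale, 80% power for the one-sided rule at 0.5 SD needs about 126 evaluable subjects in total (normal approximation), or 126/0.8 ≈ 158 randomised.

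The figures in Steps 2 to 4 come from t-tests. They do not describe the planned mixed model for fasting glucose, which both arms have at baseline, 12 and 24 weeks.

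**The case against.** The strongest reply is that Aim 2a is a prediction in a list of aims, not an analysis rule. No section says that neutrality will be declared when p exceeds 0.05. Section VII governs the analysis, lists fasting and 2-hour glucose as endpoints and compares arms. This stands in part. A reader might infer that the plan as a whole ignores the control arm for glucose. The documents do not support that: the omission is in Aim 2a alone. What remains is that Aim 2a is the only place where neutrality is given content. Nothing says Section VII replaces it, and Section VII's tests look for a difference without a margin.

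A second reply is that the size rests on assumptions. That is right: the glucose SD, the 0.5 SD effect and the correlations are not in the documents. Zero correlation is implausible because HOMA-IR is derived from fasting glucose and insulin, so 18% is an unrealistic lower end. The 9 to 12 range assumes roughly equal losses; if all five came from the treated arm, n would be 7 and the 0.5 SD figure 80%. None of this reverses the conclusion, because the plan's own detectable difference of about 1.4 SD already shows that p > 0.05 is compatible with large changes.

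A third reply is that this is a secondary aim of a pilot and no margin below about 1.4 SD is workable. That limits the severity. It also argues for dropping the neutrality claim rather than keeping the wording.

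**Conclusion.** The point holds in this form: Aim 2a and Section VII specify different contrasts, and non-significance on either would not show that Norditropin is neutral for glucose. On one measure, a real change of 0.5 SD would be non-significant 65% to 74% of the time within arm, and 82% of the time between arms at 9 v 10. The contradiction and the lack of a margin follow from the text alone. The percentages rest on the illustrative effect size, normality and near-equal losses.

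The weight is minor to moderate. A reader might infer that glucose safety is inadequately watched. The documents do not support that: fasting glucose checks, individual and study stopping rules, and a DSMB are provided separately and do not depend on Aim 2a.

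**What to change.** - **Restate Aim 2a** as the between-arm difference in change from baseline to 24 weeks, with a 95% CI, for each of the four measures.
- **Fasting glucose:** name the week-24 treatment contrast from the mixed model, since Section VII specifies only the interaction test. **2-hour glucose, HOMA-IR and Matsuda index:** use the two-sample comparison of changes.
- **Add HOMA-IR and Matsuda index** to the Section VII endpoints.
- **Do not infer neutrality from p > 0.05.** Report estimates and CIs, and state that neutrality is not established.
- **If the sponsor wants a positive claim,** fix and justify a margin in advance, say whether all four measures must meet it, and label the claim for what it is: no worsening beyond the margin if the rule is one-sided, equivalence if the CI must lie within both limits.

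This needs no extra subjects, visits or assays. The cost is that a positive claim becomes unlikely: with no true effect, a 1.0 SD margin would be met per measure 54% of the time one-sided and 35% for equivalence, and less often if all four must meet it. Without a margin, Aim 2a becomes an estimation aim, which suits a pilot.
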